6.8.1 Timing

The AEs occurring during the study must be documented, regardless of the assumption of a causal relationship. AEs should be documented from the time the subject signs and dates the patient consent form until subject participation in the study has been completed. If a subject has one or more ongoing AEs at the time of study completion, the subject must be followed and provided appropriate medical care until the sign(s) and/or symptoms(s) of the AE have remitted or stabilized in the opinion of the Investigator.

When recording an AE, the following information should be provided on the study AE eCRF:

1. Action Taken with Study Drug:

- None
- Investigational Product Discontinued

2. Other Action Taken:

- None
- Non-Drug Therapy
- New OTC or Rx Drug Added
- Hospitalized less than 24 hours

- Hospitalized greater than or equal to 24 hours

3. Outcome of an adverse event is coded as:

- Fatal
- Not Recovered/Not Resolved
- Recovered/Resolved
- Recovered/Resolved with sequelae
- Recovering/Resolving
- Unknown/Lost to follow-up

6.8.2 Severity

Severity of an AE is defined as a qualitative assessment of the level of discomfort or the degree of intensity of an AE as determined by the Investigator or reported to him/her by the subject. The assessment of severity is made irrespective of study medication relationship or seriousness of the event and should be evaluated according to the following scale:

1 = Mild: present and noticeable, but not distressing, and no disruption of normal daily activities.

2 = Moderate: bothersome, discomfort sufficient to possibly reduce or affect normal daily activity.

3 = Severe: incapacitating, with inability to work or perform normal daily activity.

A change in severity for a reported AE will require a stop date for the previous severity and a new start and stop date for the new severity. For example, a change in severity may go from mild to severe or from severe to moderate. In both cases, the start and stop dates should be recorded.

Please note: a severe AE is not the same as a serious AE. Seriousness of an AE (NOT severity) serves as a guide for defining regulatory reporting obligations (see Section [6.8.7.1](#) for further information on serious AEs [SAEs]).

6.8.3 Relationship

The study medication relationship for each AE/adverse reaction should be determined by the Investigator using these explanations:

- **Not Related:** The event is clearly related to other factors such as subject's clinical condition; therapeutic interventions, concomitant disease or therapy administered to the subject and does not follow a known response pattern to the product.

- **Unlikely Related:** The event is most probably caused by other etiologies such as participant's underlying condition, therapeutic intervention, or concomitant therapy; or the delay between administration and the onset of the AE is incompatible with a causal relationship. Therefore, there is not a reasonable possibility that the AE was caused by the study medication.
- **Possibly Related:** The event follows a reasonable, temporal sequence from the time of study medication administration and/or follows a known response pattern to the study medication, but could have been produced by other factors such as the subject's clinical state, therapeutic interventions or concomitant therapy administered to the subject.
- **Related:** The event follows a reasonable, temporal sequence from the time of study medication administration and/or follows a known response pattern to the study medication and cannot be reasonably explained by other factors such as subject's clinical state, therapeutic interventions or concomitant therapy administered to the subject, and either occurs immediately following study medication administration, or improves on stopping the study medication, or reappears on repeat exposure, or there is a positive reaction at the application site.

6.8.4 Expectedness

Since there is currently no human experience with AR-1105, expectedness of AEs that may be associated with AR-1105 are based on pre-clinical data with this product, and published data on OZURDEX.

Intravitreal injections have been associated with the risk of infection, inflammation, increased IOP and retinal detachment. It is required that AR-1105 will be administered using good sterile technique and that the subject will be adequately anesthetized, but there will still be inherent risk associated with the procedure, including endophthalmitis and injection-site reactions (pain, inflammation).

The most-common events noted in studies with rabbits and monkeys were conjunctival changes and vitreous hemorrhage associated with the procedure. Additionally, ocular discharge and eye discoloration were observed but were not deemed to be AEs. No post-injection changes were observed in the retina, or in IOP. Other findings during follow-up were consistent with known class-effects of corticosteroids, including decreased white blood cell counts, decreased blood concentrations of urea, creatinine and phosphorus, and adrenal cortical atrophy.

In the [PI](#) and [SmPC](#) for OZURDEX the most commonly-reported AEs during clinical trials are listed as increased IOP and conjunctival hemorrhage. Other AEs reported included eye pain, conjunctival hyperemia, ocular hypertension, cataract, vitreous detachment, visual disturbance and vitreous floaters and headache. Adverse events reported during the studies that were associated with the procedure, rather than the implant or dexamethasone treatment

included vitreous hemorrhage, vitreous opacity, eye pain, photopsia, conjunctival edema, anterior chamber cells and conjunctival hyperemia.

6.8.5 Clinical Significance

Determination of the significance of any AE for a particular subject, and in the context of the entire study, is the responsibility of the Investigator. The Sponsor additionally has overall responsibility for the safety of all subjects, and timely documentation and reporting of any safety concerns.

6.8.6 Clinical Laboratory Adverse Events

Clinical laboratory values (other than pregnancy tests results) that are noted as abnormal and clinically significant at study exit and that are changes from Screening values will be documented as AEs.

6.8.7 Serious Adverse Events, Serious Suspected Adverse Events, Serious Unexpected Suspected Adverse Events

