6.8 Performing Adverse Event (AE) Assessments

This includes assessment of AE severity and relationship to investigational product. AE information may be volunteered by the subject or solicited by study personnel through non-leading questions.

All AEs occurring during the study, regardless of the assumption of causal relationship, must be documented on the respective case report form (CRF). Adverse events should be documented from the time the subject signs the informed consent until 30 days after the subject's last study visit.

If a subject has an ongoing AE at the time of study completion, the ongoing AE must be followed-up and provided appropriate medical care until the event has resolved or stabilized.

Documentation of AEs/adverse reactions includes start date and stop date, severity, action(s) taken, seriousness and outcome.

The following definitions of terms apply to this section:

- *Adverse event (AE)*. Any untoward medical occurrence associated with the use of a drug in humans, whether or not considered drug related.
- *Suspected adverse reaction (SAR)*. Any AE for which there is a reasonable possibility that the drug caused the AE. For the purposes of IND safety reporting, “reasonable possibility” means there is evidence to suggest a causal relationship between the drug and the AE. Suspected adverse reaction implies a lesser degree of certainty about causality than adverse reaction, which means any AE caused by a drug.
- *Life-threatening AE or life-threatening SAR*. An AE or SAR is considered “life-threatening” if, in the view of either the Investigator or Sponsor, its occurrence places the patient at immediate risk of death. It does not include an AE or SAR that, had it occurred in a more severe form, might have caused death.

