At these visits, the subject will be queried regarding any changes to their ocular or medical health status since the previous visit, and also if there have been any changes to their ongoing medications or procedures. Vital signs (heart rate and blood pressure) will be collected. Blood samples will be collected (Month 1 and Month 2 visits only) for laboratory assessment of clinical chemistry and hematology.

The following assessments will be conducted OU:

- BCVA by ETDRS will be conducted following manifest refraction
- Slit-lamp biomicroscopy
- IOP measured using a Goldmann applanation tonometer

Following mydriasis, the following procedures will be performed OU, unless otherwise specified:

- SD-OCT (study eye)
- Fundus examination
- The implant will be viewed to verify its status. (study eye)

7.2.4 Visit 6 ([REDACTED] ± 3 Days) and Visit 9 ([REDACTED] ± 3 Days) Procedures

At these visits, the subject will be queried regarding any changes to their ocular or medical health status since the previous visit, and also if there have been any changes to their ongoing medications or procedures. Vital signs (heart rate and blood pressure) will be collected.

Blood samples will be collected for laboratory assessment of clinical chemistry and hematology and if the subject is a female of child-bearing potential, a urine pregnancy test should be administered (Visit 9 only).

The following procedures will be conducted OU:

- BCVA by ETDRS will be conducted following manifest refraction
- Slit-lamp biomicroscopy examination
- Gonioscopy (study eye)
- IOP measured using a Goldmann applanation tonometer

Following mydriasis, the following procedures will be performed OU unless otherwise noted:

- SD-OCT (study eye)
- Fundus examination (study eye)
- Fluorescein angiography
- 3-field fundus photography (study eye)
- The implant will be viewed to verify its status (study eye)

If residual implant is still visible in the vitreous at the Month 6 visit, the subject will be required to return to the site at Month 7 for safety follow-up. Otherwise, the Month 6 visit will be the final visit, and the subject should be thanked for their participation in the study.

7.3 [REDACTED] or Early Termination Procedures

Procedures that should be conducted in the event that the subject needs to exit the study prior to Month 6 (Visit 9) are provided above in Section [7.2.4](#).

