9.5 Primary Safety Assessments and Analyses

The primary safety analysis will summarize ocular and non-ocular treatment-emergent adverse events (TEAEs) using discrete summaries at the subject level by system organ class and preferred term for each treatment group. Ocular TEAEs will be summarized separately for all study and fellow eyes. A TEAE will be defined as occurring after the first dose of study medication. Serious adverse events and treatment-related ocular and non-ocular TEAEs will be summarized similarly. Ocular and non-ocular TEAEs will also be summarized by severity.

Slit lamp biomicroscopy and dilated indirect ophthalmoscopy measures will be summarized at each visit using discrete summary statistics.

Intraocular pressure will be summarized at each visit, using continuous and discrete summary statistics, including change from baseline and the proportion of study eyes with an increase from baseline in IOP of 10 mmHg or more and the proportion of study eyes with IOP of 30 mmHg or more.

Vital signs and safety laboratory data will be summarized at each visit, using continuous summary statistics, including change from baseline.

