2.1 Primary Variables

The primary variables are related to safety and include the following:

- Ocular and non-ocular treatment-emergent adverse events (TEAE)
- Slit lamp biomicroscopy
- Dilated indirect ophthalmoscopy measures
- Intraocular pressure (IOP), including change from baseline and the proportion of study eyes with an increase from baseline in IOP of 10 mmHg or more and the proportion of study eyes with IOP of 30 mmHg or more.
- Vital signs
- Safety laboratory data

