15.1 Adverse Events

An AE is defined as any untoward medical occurrence associated with the use of a drug in humans, whether or not the event is considered drug-related. An AE can therefore be any unfavorable and unintended sign (e.g., an abnormal laboratory finding), symptom, or disease occurring after informed consent form is signed and dated, without any judgment about causality. Any pre-existing medical condition that worsens after first administration of the study medication will also be considered a new AE. The AE reporting period starts from the time the subject signs and dates the informed consent and until 30 days after the subject's last study visit. All Aes will be coded using the MedDRA 21.1.

Treatment-emergent adverse events are defined as any event that occurs or worsens on or after the study treatment is initiated. Adverse events recorded in the eCRF which began prior to treatment will not be included in the summary tables but will be included in the AE data listings.

An overall summary will be presented that includes the number of TEAEs and the number and percentage of subjects who experienced at least one TEAE, by treatment group. This summary will also include breakdowns of TEAEs further categorized as ocular (study eye, fellow eye, and both eyes separately) or non-ocular, serious TEAEs, TEAEs by maximum severity, TEAEs by maximum relationship to study medication, TEAEs by maximum relationship to study procedure, TEAEs by maximum expectedness, number of serious TEAEs, number of subjects with any serious TEAEs, and with TEAEs leading to death.

Additional summaries of TEAEs will be provided showing the number and percentage of subjects who experienced at least one TEAE. These summaries will be presented by system organ class (SOC) and preferred term (PT). Non-ocular TEAEs will be summarized using discrete summary statistics and presented by treatment group at the subject level by SOC and PT. Ocular TEAEs will be similarly summarized at the subject level for study eyes, fellow eyes, and both eyes separately. If a subject reports the same PT multiple times within the same SOC, that PT will only be reported once within that SOC. As with the PT, if a subject reports multiple conditions within the same SOC, that SOC will only be reported once. In the summary, SOC will be listed in ascending alphabetical order; PTs will be listed in order of descending frequency for all subjects within each SOC.

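### Protocol 6.8.6 ties laboratory AEs to study exit, which conflicts with Protocol 6.8 and SAP 15.1 and can under-count laboratory TEAEs at earlier visits

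*Protocol*

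**What the plan says.** The laboratory-specific rule is in Protocol 6.8.6: values other than pregnancy tests that are "noted as abnormal and clinically significant at study exit and that are changes from Screening values will be documented as AEs". It is the only rule in the protocol or SAP that says when a laboratory result becomes an AE.

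Two general statements are wider:

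- Protocol 6.8: "All AEs occurring during the study, regardless of the assumption of causal relationship, must be documented", running from consent.
- SAP 15.1: an AE can be "any unfavorable and unintended sign (e.g., an abnormal laboratory finding), symptom, or disease occurring after informed consent form is signed and dated".

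On sampling, Protocol 7.2.3 states: "Blood samples will be collected (Month 1 and Month 2 visits only) for laboratory assessment of clinical chemistry and hematology". The schedule tables (Protocol Table 1, SAP Table 2) show laboratory tests at Screening, Visit 4, Visit 5 and Visit 9, and none at Visits 10 to 12. Protocol 7.4 lists no blood draw for the Month 7 to 9 visits.

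On analysis, Protocol 9.5 opens with: "The primary safety analysis will summarize ocular and non-ocular treatment-emergent adverse events (TEAEs) using discrete summaries at the subject level". It then has laboratory data summarised at each visit. SAP 2.1 begins "The primary variables are related to safety and include the following", and its list includes both TEAEs and safety laboratory data. SAP 15.5 gives observed values, changes and shifts from baseline to each post-baseline visit, with listings that mark abnormal values.

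**The concern.** A rule that names one time point suggests to a site that other time points are not triggers. An investigator who judges a Month 1 result clinically significant, and sees it normal again by Month 6, could follow 6.8.6 and record no AE. Another could follow 6.8 and record one. With about 20 sites planned, laboratory AE counts could then depend partly on which section a site follows.

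This is the first human exposure to the product, and safety through Month 6 feeds the choice of formulation (Protocol 3.1). Laboratory effects are plausible. Of the animal studies, Protocol 6.8.4 says: "Other findings during follow-up were consistent with known class-effects of corticosteroids, including decreased white blood cell counts", and it goes on to name lower urea, creatinine and phosphorus. An unrecorded event has no TEAE entry and no investigator assessment of severity, relationship or outcome.

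**Working it through.** **1. Coverage by visit.** Visits are mapped to months by the protocol's table of contents. Draws come from the schedule tables and Protocol 7.2.3, 7.2.4 and 7.4.

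| Visit | Scheduled draw | 6.8.6 read literally | SAP 15.5 summaries and shifts |
|---|---|---|---|
| Month 1 (V4) | Yes | Outside | Inside |
| Month 2 (V5) | Yes | Outside | Inside |
| Month 3 (V6) | None in the tables; 7.2.4 can be read as yes | Outside | Inside if drawn |
| Month 6 (V9) | Yes | Inside if this is the exit visit | Inside |
| Months 7–9 (V10–V12) | None | No result to apply it to | Nothing to summarise |

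By the schedule tables, 2 of 3 post-dose draws fall outside the literal rule. If 7.2.4 does mean a Month 3 draw, it is 3 of 4. Early termination is covered, because Protocol 7.3 refers to the 7.2.4 procedures, which include a sample.

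For a subject followed past Month 6 there are two readings. If exit is the last visit (Protocol 7.4), none of the scheduled post-dose draws is at exit. If exit is taken as Month 6, where Protocol 6.10.1 defines completion, the count is the same as for other subjects.

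**2. What the by-visit tables replace.** SAP 15.5 classifies values against the normal range. It plans no tabulation by the investigator's judgement of clinical significance, whereas SAP 15.2 grades slit-lamp findings as clinically significant or not. Severity, relationship, action taken and outcome belong to the AE record (Protocol 6.8.1 to 6.8.3). SAP 15.5 therefore preserves the value but not the assessment.

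**3. Size of one unrecorded event.** 1/20 = 5 percentage points of TEAE incidence in a group. This holds only if the subject has no other event under the same preferred term, since SAP 15.1 counts a subject once per term.

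**4. The plan's 13.9% figure.** Protocol 9.2 and SAP 5 give it for zero events in 20 subjects: 1 − 0.05^(1/20) = 0.1391. It reproduces as the one-sided exact bound.

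That bound reads zero recorded as zero occurred. As an illustration only, suppose a share c of clinically significant laboratory events is still present at the exit sample, and only those are recorded. The documents give no value for c. The bound on true incidence becomes 0.1391/c, and the chance of recording at least one event at a true incidence of 13.9% is 1 − (1 − 0.139c)^20.

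| c (assumed) | Bound after 0 of 20 recorded | Chance of at least one record |
|---|---|---|
| 1 | 13.9% | 95.0% |
| 0.75 | 18.5% | 88.9% |
| 0.50 | 27.8% | 76.3% |
| 0.25 | 55.6% | 50.7% |

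This applies to laboratory AEs only. If sites record them from every draw, c = 1 and the plan's figure stands.

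**The case against.** The strongest reply is that 6.8.6 does not say *only*. It can be read as a floor: exit values that meet the test must be recorded, while the general duty in 6.8, repeated in 6.8.1, covers earlier ones. A separate Laboratory Manual, not available here, might also give instructions. This stands as far as it shows that under-recording is one reading and not a requirement. It does not remove the conflict. The AE definition in Protocol 6.8 does not mention laboratory findings, and the SAP, which does, can only analyse what sites record under the protocol.

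Four stronger readings are tempting, and the documents do not support them:

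- *Month 1 and 2 effects stay out of the primary safety data.* They do not. No single primary safety endpoint is defined; laboratory data are a primary variable in SAP 2.1 and are analysed at each visit.
- *The missed effects are transient steroid effects.* Protocol 6.8.4 reports animal findings with no time course.
- *Serious laboratory events would be missed.* SAE reporting under Protocol 6.8.7.1 does not depend on 6.8.6.
- *One missed event makes the 13.9% statement false.* That figure is a sample-size justification, and the SAP plans no such conclusion for each AE type. A missed event would remove the stated confidence for that laboratory AE, but the true incidence could still be below 13.9%.

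**Conclusion.** The point holds as an inconsistency that should be corrected. Read literally, 6.8.6 gives no AE trigger for two of the three scheduled post-dose laboratory draws. For subjects who exit at Months 7 to 9 there is no exit sample to which the rule could apply. The result can be an under-count of laboratory TEAEs and the loss of the investigator's assessment of them. The laboratory values remain in the primary safety variables.

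The effect on any one incidence is 5 percentage points per affected subject in a group of 20. How many subjects would be affected cannot be derived from the documents: it depends on how sites read 6.8.6 and on how many abnormalities resolve before exit. The illustration with c shows direction and range and is not an estimate.

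**What to change.** In Protocol 6.8.6, replace *at study exit* with *at any post-treatment laboratory assessment, scheduled, unscheduled or at early termination*. Keep the conditions of clinical significance and of a change from Screening. The rule then agrees with Protocol 6.8 and SAP 15.1, and the meaning of exit for subjects followed past Month 6 no longer matters.

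In the same edit, reconcile Protocol 7.2.4 with the schedule tables on whether blood is drawn at Month 3. Wording the rule as any assessment makes it correct whichever way that is settled.

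The cost is one phrase in an amendment or site instruction. No blood draw is added and no clinical rule changes. The downside is a few more AE records and slightly higher reported AE rates.

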6.8.7.1 Reporting Serious Adverse Events (SAEs) or Serious Suspected Adverse Reactions (SSARs)

An Investigator must immediately report any SAE or SSAR (see Section 6.8 for definitions) to the Sponsor or Sponsor representative using the SAE report form, whether or not considered drug-related, including those listed in the protocol or IB and must include an assessment of whether there is a reasonable possibility that the drug caused the event. The Investigator must report any SAE or SSAR that occurs during the course of the study or within 4 weeks of last study visit. In case of incomplete information, the Investigator must provide follow-up information as soon as possible, again using the SAE report form.

In addition, in the case of immediately life-threatening AEs or AEs with fatal outcome, or AEs that are serious, unexpected (i.e., not in the Clinical Investigator's Brochure) and judged related to the investigational product, or a loss in BCVA ≥ 3 lines, the Investigator must inform the Sponsor or Sponsor representative by phone within 24 hours of observation or occurrence of the SAE.

Pregnancies occurring in subjects enrolled in the study or in their partners, occurring up to 30 days after the subject's last study visit, must be reported and followed to outcome. While pregnancy itself is not considered to be an AE or SAE, pregnancy reports are tracked by the study Medical Monitors. Premature terminations including miscarriage, spontaneous abortion, or elective termination of a pregnancy for medical reasons will be reported as an SAE. Other pregnancy complications should be reported as SAEs, if they meet serious criteria. Should a pregnancy result in a congenital anomaly or birth defect, a separate SAE report must be submitted for the baby. Furthermore, all neonatal deaths that occur within 30 days of the birth should be reported as SAEs, without regard to causality.

The Investigator must complete the pregnancy report form and fax or email the form to the study Medical Monitors within 1 business day of knowledge of the pregnancy. Following delivery or termination of pregnancy, the pregnancy report form is to be completed and submitted by fax or email to the Medical Monitors for the study.

SAEs must be reported to the IRB/IEC according to the IRB/IEC requirements.

The contact information of the study Medical Monitors is as follows:

